5.2 Safety Analysis Set

The safety analysis set includes all subjects who were administered at least 1 dose of double-blind IMP.

5.3 Handling of Missing Data

For the primary endpoint analysis, a mixed-model repeated measures (MMRM) analysis will be performed using the observed cases (OC) dataset without imputation of missing data on an assumption of missing at random (MAR). Placebo multiple imputation and tipping point analysis on an assumption of missing not at random (MNAR) will be performed as a sensitivity analysis for handling of missing data.

The secondary endpoint analyses (MADRS response rate, MADRS remission rate, Clinical Global Impression – Improvement [CGI-I] improvement rate, CGI-I score, mean change from baseline in HAM-D 17-item total score, and mean change from baseline in Apathy Scale total score) and the safety analysis (body weight, body mass index [BMI], and waist circumference) will be performed using data imputed with the last data after the start of double-blind IMP administration (last observation carried forward [LOCF]).

6 Primary and Secondary Outcome Variables

6.1 Primary Outcome Variables

The primary endpoint is the change from baseline in MADRS total score at Week 6 of the double-blind treatment period, and the mean change in the OPC-64005 20-mg group will be compared with that in the placebo group.

6.2 Secondary Outcome Variables

The secondary endpoints are the MADRS response rate (proportion of subjects with $\geq 50\%$ reduction from baseline in MADRS total score at Week 6 of the double-blind

treatment period), MADRS remission rate (proportion of subjects with MADRS total score ≤ 10 and $\geq 50\%$ reduction from baseline in MADRS total score at Week 6 of the double-blind treatment period), CGI-I improvement rate (proportion of subjects with CGI-I of 1 or 2 at Week 6 of the double-blind treatment period), mean change from baseline in Clinical Global Impression – Severity of Illness (CGI-S), mean change from baseline in HAM-D 17-item total score, mean change from baseline in Apathy Scale score, mean change from baseline in the total score of MADRS-S (total score of Items 1 through 9), and mean change from baseline in MADRS anhedonia factor score for evaluation of the efficacy of OPC-64005 at 20 mg.

7 Disposition and Demographic Analysis

7.1 Subject Disposition

The numbers and proportions of subjects from whom informed consent was obtained, screen failures, those treated with IMP in the placebo lead-in period, those who completed the placebo lead-in period, those who discontinued treatment in the placebo lead-in period, and those who discontinued treatment in the placebo lead-in period by reason for discontinuation will be summarized.

The numbers and proportions of randomized subjects in the double-blind treatment period, those treated with IMP in the double-blind treatment period, those who completed the double-blind treatment period, those who discontinued treatment in the double-blind treatment period, those who discontinued treatment in the double-blind treatment period by reason for discontinuation, and those included in each analysis set will be summarized for overall, for each treatment group, and for the overall OPC-64005 group.

The numbers of subjects treated with IMP in the double-blind tapering period in the all subjects, in those who completed the double-blind tapering period, and in those who discontinued treatment in the double-blind treatment period will be summarized for overall, for each treatment group, and for the overall OPC-64005 group.

The numbers and proportions of subjects who completed the double-blind treatment period will be summarized by time point (Day) (1-7, 8-14, 15-21, 22-28, 29-35, 36-42, and > 42), for overall, for each treatment group, and for the overall OPC-64005 group.

7.2 Demographic and Baseline Characteristics

Descriptive statistics (mean, standard deviation, minimum, median, and maximum; hereinafter the same applies) of age, height, body weight, waist circumference, and BMI and frequency distribution of sex, race, ethnicity, country, medical history (yes or no), complications (yes or no), and cytochrome P450 (CYP) 2D6 genotype (phenotype) will

be determined for overall, for each treatment group, and for the overall OPC-64005 group in each analysis set in the double-blind treatment period. Baseline values will be used for body weight, waist circumference, and BMI.

7.3 Baseline Disease Evaluation

Descriptive statistics of the duration (in months) of the current major depressive episode, age at initial onset, duration (in months) of major depression from initial onset, MADRS total score, HAM-D 17-item total score, CGI-S, Apathy Scale total score, MADRS-S total score, and MADRS anhedonia factor score and frequency distribution of DSM-5 diagnosis (single episode, recurrent episode), DSM-5 severity (mild, moderate, severe), specifiers (not applicable, applicable, applicable if [with anxious distress, with mixed features, with melancholic features, with atypical features, with mood-congruent psychotic features, with mood-incongruent psychotic features, with catatonia, peripartum onset, seasonal pattern]), number of major depressive episodes (1, 2, 3, 4, ≥ 5), MADRS total score (< 30 , ≥ 30), prior medications (antidepressants) for the current major depressive episode, prior medications (antianxiety agents), and prior medications (hypnotic agents) will be determined for overall, for each treatment group, and for the overall OPC-64005 group in each analysis set in the double-blind treatment period.

Baseline values will be used for MADRS total score, HAM-D 17-item total score, CGI-S, Apathy Scale total score, MADRS-S total score, and MADRS anhedonia factor score.

The duration of the current major depressive episode and the duration of major depression from initial onset will be determined using the following formula: Duration (in months) = (date of demographic assessment – date of onset + 1) /30. Any unknown month or day of onset will be replaced with June or 15, respectively.

7.4 Treatment Compliance

The compliance rate (the number of days that the subject took medication / the number of days for which the IMP was prescribed) in the double-blind treatment period will be classified into $< 70\%$, $\geq 70\%$ to $< 80\%$, $\geq 80\%$ to $< 90\%$, and $\geq 90\%$, and frequency distribution of the compliance rate will be determined for overall, for each treatment group, and for the overall OPC-64005 group in FAS. The same tabulation will be performed for the placebo lead-in period and double-blind tapering period. Subjects without dose tapering will be classified as “not applicable” in tabulation for double-blind tapering period.

7.5 Prior and Concomitant Medications

The number and proportion of subjects who used prior medications (antidepressants) for the current major depressive episode will be determined by drug for overall, for each treatment group, and for the overall OPC-64005 group in the safety analysis set.

The numbers and proportions of subjects who used medications before, during, and after the double-blind treatment period will be determined by drug class and preferred term of the World Health Organization Drug Dictionary (WHODD) version September 1, 2019 for overall, for each treatment group, and for the overall OPC-64005 group in the safety analysis set.

7.6 Protocol Deviations

The number and proportion of randomized subjects with major deviations from the protocol will be determined by deviation category (IMP administration, eligibility criteria, failure to discontinue the trial when the subject meets the withdrawal criteria, procedural deviation that may affect primary endpoint evaluation, prohibited concomitant medications, and overall) and trial site for overall, for each treatment group, and for the overall OPC-64005 group.

The same tabulation will be performed for all subjects who are not randomized.

8 Efficacy Analysis

The efficacy analysis will be performed on the FAS. Baseline is the last data obtained after the start of IMP administration in the placebo-lead in period and before the start of double-blind IMP administration.

8.1 Primary Efficacy Endpoint

The primary endpoint is the change from baseline in MADRS total score at Week 6 of the double-blind treatment period.

8.1.1 Primary Efficacy Analysis

For the primary analysis, an MMRM analysis will be performed using the OC dataset of the FAS.

The MMRM will include treatment group (OPC-64005 10-mg group, OPC-64005 20-mg group, and placebo group), time point (double-blind treatment period Weeks 1, 2, 3, 4, 5, and 6), and interaction between treatment group and time point as factors, and baseline and interaction between baseline and time point as covariates. An unstructured error variance-covariance structure will be assumed. For degree-of-freedom approximation, the

Kenward-Roger method will be used. The statistical comparison between the OPC-64005 20-mg group and the placebo group will be performed based on differences in the least square means at Week 6 of the double-blind treatment period between the 2 groups. If any problem occurs in the convergence status in the estimation of variance components, error variance-covariance structures of heterogeneous toeplitz, heterogeneous autoregressive of order 1, and heterogeneous compound symmetry will be applied in this order, and the first converged structure will be used in the primary analysis. If structures other than unstructured are selected, sandwich estimators of standard error will be used.

For each time point, the least square mean of each treatment group and the differences in the least square means between each OPC-64005 group and the placebo group, as well as the two-sided 95% confidence intervals (CIs), will be determined.

The time course of the least square means of the change from baseline in MADRS total score and standard errors will be plotted for each treatment group.

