Assessments for efficacy: MADRS, Clinical Global Impression – Improvement (CGI-I), Clinical Global Impression – Severity of Illness (CGI-S), HAM-D, MADRS-S, and Apathy Scale

Assessments for pharmacokinetics, pharmacogenomics, and future biospecimen research: Plasma PK assessment, cytochrome P450 (CYP) 2D6 genetic testing, and blood sampling for DNA storage

Assessments for safety: Laboratory tests, vital signs, physical examination, height, body weight, waist circumference, 12-lead electrocardiogram (ECG), pregnancy test, Columbia-Suicide Severity Rating Scale (C-SSRS), and adverse events (AEs)

Screening/Other: Medical and treatment history, etc

Data Monitoring Committee: No

Statistical Methods:

Statistical Methods for Primary Endpoint:

The primary endpoint is the change from baseline in MADRS total score at Week 6 of the double-blind treatment period.

For the primary analysis, mixed-model repeated-measure (MMRM) analysis will be performed using the observed cases dataset of the full analysis set.

The MMRM will include treatment group (OPC-64005 10-mg group, OPC-64005 20-mg group, and placebo group), timepoint (double-blind treatment period Weeks 1, 2, 3, 4, 5, and 6), and interaction between treatment group and timepoint as factors, and baseline and interaction between baseline and timepoint as covariates. An unstructured error variance-covariance structure will be assumed. For degree-of-freedom approximation, the Kenward-Roger method will be used. The statistical comparison will be performed based on differences in the least square means at double-blind treatment period Week 6 between the OPC-64005 20-mg group and the placebo group.

For each timepoint, the least square mean of each treatment group and the differences in the least square means between each OPC-64005 group and the placebo group, as well as the two-sided 95% confidence intervals, will be determined.

Rationale for target number of subjects:

As no clinical trials of OPC-64005 in patients with major depressive disorder have been previously conducted, the target number of subjects was determined based on the results from another antidepressant clinical trial using MADRS score as the primary endpoint.

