6.3 Measures to Minimize/Avoid Bias

This trial will be performed as a randomized double-blind trial to minimize bias.

Treatment assignment codes will not be disclosed to the subjects or investigator. Except for designated persons, the treatment assignment code will not be disclosed to the sponsor's trial staff including contract research organizations (CROs) (except for the bioanalytical laboratory and pharmacogenomic [PGx] laboratory) during the trial.

Emergency keys are controlled by the IRT system until the end of the trial. They will be disclosed according to the procedures for breaking the blind when a medical emergency occurs to a subject and it is judged important to identify the treatment assignment code for treatment of the subject. Procedures for breaking the blind can be found in Section 8.8.7.

If the IMP is collected by the sponsor before unblinding, the IMP will be collected in the sealed state.

Subjects will be assigned to the OPC-64005 10-mg group, OPC-64005 20-mg group, or placebo group at a ratio of 1:4:4 using the dynamic allocation method (minimization method). A separate specification will be developed to provide details.

Results of drug concentration measurement and PGx assessment should be retained in a manner that prevents their disclosure until unblinding at the end of the trial. These tests

will be performed by the specified laboratories, and will not be performed at a clinical laboratory of the trial site.

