8.1.2 Sensitivity Analyses

8.1.2.1 Sensitivity Analysis for Handling of Missing Data

As a sensitivity analysis for handling of missing data, placebo multiple imputation and tipping point analysis on MNAR assumption will be performed using a pattern-mixture model with multiple imputation.

Multiple imputation analysis will be performed according to the following procedure. The number of imputations will be 100.

- 1) The Markov Chain Monte Carlo (MCMC) method will be used to impute intermittent missing data to produce a monotone missing data pattern.
- 2) The monotone regression method will be used to impute monotone missing data.
- 3) The same MMRM as that of the primary efficacy analysis will be used to analyze the multiple-imputed datasets.
- 4) The MIANALYZE procedure will be used to integrate the analysis results of the multiple-imputed datasets, and the estimate of the difference between the OPC-64005 20-mg group and the placebo group at Week 6 in the double-blind treatment period and its 95% CI and p-value will be determined.

In placebo multiple imputation, for discontinued subjects in each OPC-64005 group, MNAR will be assumed for missing data after discontinuation and an imputation model based on the placebo group will be used in imputation.

In tipping point analysis, for subjects in each OPC-64005 group who discontinued treatment for any of the following reasons, MNAR will be assumed for missing data after discontinuation.

- Withdrawal for any reason
- Withdrawal due to AEs, a lack of efficacy, or consent withdrawal
- Withdrawal due to AEs or a lack of efficacy

For subjects in each OPC-64005 group who discontinued treatment for reasons assumed as MNAR, the MAR assumption will be used to impute post-discontinuation missing data, add Δ (intergroup differences in MMRM of the primary efficacy analysis) \times k% to the imputed value, and increase k until a statistically significant conclusion is reversed ($p > 0.05$).

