8.1.2.2 Sensitivity Analysis for Normality Assumption

As a sensitivity analysis for normality assumption, multiple imputation under the MAR assumption will be performed, and the Wilcoxon rank sum test will be used to compare the OPC-64005 20-mg group and the placebo group for each time point, and the Hodges-Lehmann estimator of the intergroup difference will be determined. A robust regression analysis with treatment group as a factor and baseline as a covariate will also be performed for each time point. If between-imputation variance is 0 because of the absence or paucity of missing data, analysis without multiple imputation will be performed.

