8.1.3 Technical Computational Details for Primary Efficacy Analysis

The SAS code for the MIXED procedure to perform the primary efficacy MMRM analysis is shown below.

```
proc mixed;
  class treatment visit subjid;
  model change=treatment baseline visit treatment*visit baseline*visit / ddfm=kr;
  repeated visit /type=un subject=subjid;
  lsmeans treatment*visit / diff cl;
  ods output diffs=diffs lsmeans=lsmeans;
run;
```

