8.2 Secondary Efficacy Analyses

The secondary endpoint analysis will be performed on the FAS.

- MADRS response rate
- MADRS remission rate
- CGI-I improvement rate

The MADRS response rate in the OPC-64005 20-mg group will be compared with that in the placebo group using the χ^2 test in the LOCF dataset. The differences in the response rates between each OPC-64005 group and the placebo group, as well as the two-sided 95% CI (Wald confidence interval), will be determined. The MADRS remission rate and CGI-I improvement rate will be analyzed in the same manner as the MADRS response rate. The same analysis will be performed on the OC dataset.

- Mean change from baseline in HAM-D 17-item total score
- Mean change from baseline in Apathy Scale score

An analysis will be performed on the mean change from baseline in HAM-D 17-item total score using the analysis of covariance (ANCOVA) model with treatment group as a factor and baseline as a covariate in the LOCF dataset. The least square means of each treatment group and the difference in the least square means between each OPC-64005 group and the placebo group, as well as the two-sided 95% CIs, will be calculated. The mean change from baseline in Apathy Scale total score will be analyzed in the same manner as the mean change from baseline in HAM-D 17-item total score. The same analysis will be performed on the OC dataset.

- Mean change from baseline in CGI-S
- Mean change from baseline in MADRS-S total score (total score of Items 1 through 9)
- Mean change from baseline in MADRS anhedonia factor score (total score of MADRS Items 1, 2, 6, 7, and 8)

The MMRM analysis will be performed in the same manner as that for the primary endpoint.

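### Allocation is by minimisation, but the primary MMRM adjusts only for baseline MADRS; if another allocation factor explains up to an assumed 10% of the remaining Week 6 variance, the standard error is 0% to about 5% too wide (a minor loss of efficiency)

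*SAP*

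**What the plan says.** Protocol 6.3 assigns subjects to 10 mg, 20 mg and placebo "at a ratio of 1:4:4 using the dynamic allocation method (minimization method"), and adds: "A separate specification will be developed to provide details". Neither the protocol nor the SAP names a minimisation factor.

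The primary model is the same everywhere it appears. SAP 8.1.1 lists treatment, time point, "interaction between treatment group and time point as factors, and baseline and interaction between baseline and time point as covariates". The Protocol Synopsis has the same terms, "interaction between treatment group and timepoint as factors, and baseline and interaction between baseline and timepoint as covariates", and Protocol 9.4.1.1 agrees. The SAS statement in SAP 8.1.3 is "model change=treatment baseline visit treatment*visit baseline*visit / ddfm=kr".

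No other planned analysis adds the allocation factors:

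- The multiple-imputation analyses in SAP 8.1.2.1 repeat the primary model: "The same MMRM as that of the primary efficacy analysis will be used to analyze the multiple-imputed datasets".
- SAP 8.1.2.2 has "A robust regression analysis with treatment group as a factor and baseline as a covariate will also be performed for each time point".
- The HAM-D and Apathy Scale ANCOVAs in SAP 8.2 use "treatment group as a factor and baseline as a covariate in the LOCF dataset".
- The subgroup analyses in SAP 8.3 fit the model within each subgroup and do not adjust the overall comparison.
- SAP Section 14 records one change, the tabulation of CYP2D6 phenotype, and gives no reason for leaving the allocation factors out.

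**The concern.** Minimisation forces the arms to be alike on the chosen factors, so those factors contribute little to the chance variation of the treatment difference. A model that omits them still counts their variance as error. Its standard error then describes a less balanced design than the one that was run: it is too large, the confidence interval is too wide and the test is conservative. The precision bought by balancing is partly thrown away.

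This matters only if at least one factor is something other than baseline MADRS and predicts the Week 6 score after baseline MADRS is accounted for. The documents settle neither condition. What is at stake is a little precision on the single primary test.

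**Working it through.** **Inputs.** From Protocol 9.1 and SAP Section 4: difference 4, SD 11, two-sided 5% level, 80% power, 120 per arm for 20 mg and placebo, 30 for 10 mg, 270 in total. From Protocol 6.3: minimisation, 1:4:4. Assumed, because the documents give no value: R², the share of Week 6 variance left after baseline MADRS that the other factors explain, at 0%, 2%, 5% and 10%. SD 11 is treated as the SD left after baseline; the standard-error ratio does not depend on this.

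**The plan's own figure.** The normal approximation gives 119 per arm. The two-sided t-test has 79.8% power at 119 and 80.1% at 120, so 120 per arm is reproduced. The standard error is 11 × √(2/120) = 1.420, and normal-approximation power at 120 is 80.4%.

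**Formulas under perfect balance.** These are an upper bound on the effect.

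- Standard-error ratio, reported to true: r = 1/√(1 − R²)
- Type I error: 2Φ(−1.960 r)
- Power without the factors: Φ((4/1.420 − 1.960) r)
- Power with the factors: Φ(4r/1.420 − 1.960)

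At R² = 10%: r = 1/√0.90 = 1.054 and the adjusted standard error is 1.420/1.054 = 1.347. Type I error is 2Φ(−2.066) = 3.9%. Power is Φ(0.857 × 1.054) = Φ(0.903) = 81.7% without the factors and Φ(4/1.347 − 1.960) = Φ(1.009) = 84.4% with them. The 95% half-width is 1.960 × 1.420 = 2.78 against 1.960 × 1.347 = 2.64 MADRS points.

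| Assumed R² | SE ratio | Type I error | Power, unadjusted | Power, adjusted |
|---|---|---|---|---|
| 0% | 1.000 | 5.0% | 80.4% | 80.4% |
| 2% | 1.010 | 4.8% | 80.7% | 81.2% |
| 5% | 1.026 | 4.4% | 81.0% | 82.4% |
| 10% | 1.054 | 3.9% | 81.7% | 84.4% |

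**Check by simulated minimisation.** 270 subjects were allocated 1:4:4 with one binary factor (the minimising arm always followed), three factors (80%) or five factors (60%); these settings are assumptions. Week 6 was analysed by ANCOVA with treatment and baseline, with and without the factors, over 100,000 trials per setting. Ranges are across the three settings.

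| Assumed R² | SE excess, no loss | Type I error | Power, unadjusted | Power, adjusted | SE excess, 20% random loss |
|---|---|---|---|---|---|
| 2% | 0.9–1.1% | 4.7–4.9% | 80.0–80.2% | 80.5–80.8% | 0.6–0.8% |
| 5% | 2.4–2.7% | 4.4–4.5% | 80.3–80.5% | 81.7–82.0% | 1.8–2.1% |
| 10% | 5.0–5.5% | 3.8–4.0% | 80.9–81.2% | 83.7–84.0% | 3.9–4.2% |

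The gain from adjusting is about 0.6, 1.4 and 2.8 points of power. With the factors in the model, the ratio of reported to actual standard error is 0.999 to 1.001 and type I error is 5.0% to 5.1%. The 20% loss is an assumption; loss weakens the balance and so shrinks the effect.

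**Time-point interaction.** These gains come from a Week 6 analysis. In a six-visit model (assumed SD rising from 6 to 11, AR(1) correlation 0.7 or 0.85), a main effect alone recovers all of the Week 6 variance reduction if the factor's effect is constant over time. If the effect grows linearly to Week 6, it recovers only 58% to 61% (correlation 0.7) or 40% to 43% (correlation 0.85). The interaction is therefore needed to be sure of the gain.

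**The case against.** The best defence is that no defect has been shown. The loss depends on two facts outside the documents: that a factor other than baseline MADRS was used, and that it is prognostic. A reader might infer that the factors were never defined. The documents do not support that, since Protocol 6.3 assigns them to a separate specification. This part of the defence stands, and zero must be inside the stated range.

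The second argument is that the model is simple, the same in both documents, and errs on the safe side in a phase 2 exploratory trial with one primary test. The worst case modelled moves the half-width by 2.78 − 2.64 = 0.14 MADRS points. There may also be slack in the planning SD: the standard errors quoted from the escitalopram trial imply SDs from 0.8 × √118 = 8.7 to 0.9 × √125 = 10.1, below the 11 assumed, although they come from a Week 8 LOCF analysis and are only indicative. This argument rightly limits the importance of the point. It does not show a real downside to adjusting for factors that the allocation system already holds.

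Two stronger readings should also be set aside. A reader might infer that ignoring the minimisation factors makes the primary test anti-conservative or its estimate biased. The calculation shows the opposite direction for the test, and balance on an omitted factor does not bias the comparison. A reader might also infer that the trial is underpowered for this reason; unadjusted power stays at about 80% or slightly above.

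**Conclusion.** The point holds as a minor efficiency improvement, not an error. For an assumed R² of 0% to 10% beyond baseline MADRS, the primary standard error is about 0% to 5% too wide with no loss, and about 0% to 4% with 20% random loss. Two-sided type I error runs from 5% down to about 3.9%, and adjustment would gain up to about 2.8 points of power, given full recovery of the Week 6 effect.

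The range is only as good as the assumed R²: by the same formula, 15% would give 8.5% and 20% would give 11.8%. The size was computed for the primary comparison only, not for the robust regression or the HAM-D and Apathy Scale ANCOVAs, where the reasoning is the same.

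**What to change.** Before unblinding:

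- Name the minimisation factors in SAP 8.1.1.
- Add each factor not already carried by continuous baseline MADRS, with its time-point interaction as is done for baseline, to the MMRM in SAP 8.1.1 and the code in 8.1.3.
- The analyses in 8.1.2.1 then inherit the model; put the same factors in their imputation models.
- Add the factors as main effects to the robust regression in 8.1.2.2 and to the HAM-D and Apathy Scale ANCOVAs in 8.2.
- Record the change in SAP Section 14, or align Protocol 1.1 and 9.4.1.1 by amendment.
- If site is a factor, use a random effect or omit it with a stated reason, given about 100 sites for 270 subjects.
- If baseline MADRS is the only factor, say so; no model change is then needed.

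A factor-adjusted MMRM as a sensitivity analysis alone is a weaker fallback, because the primary standard error stays as it is.

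The cost is a sentence naming the factors, six model terms per binary factor (one main effect and five for the interaction over six visits), and a documented departure from the protocol's model. The amendment route also means submission to the IRB as local regulations require. The allocation system must already hold the factors, so no new data are needed and subjects are not affected.
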